4.2. Demographics and Baseline Characteristics

Demographic and baseline characteristics, baseline disease characteristics, baseline efficacy parameters, and medical history information will be summarized by treatment arm and overall. No formal statistical comparisons will be performed.

Age, height, weight, and body mass index (BMI) will be summarized using descriptive statistics (number of patients, mean, SD, median, minimum, and maximum). Sex, race, ethnicity, and region will be summarized by presenting the numbers and percentages of patients in each category.

The following baseline disease characteristics will be summarized by presenting the numbers and percentages of patients in each category:

- Age at hATTR Symptom onset [< 50 ; ≥ 50]
- Neuropathy Impairment Score (NIS) [< 50 ; ≥ 50 & < 100 ; ≥ 100]
- Genotype [V30M; non-V30M]
- Early onset V30M [< 50 years of age at onset] vs. all other mutations [including late onset V30M]
- Previous tetramer stabilizer use [tafamidis or diflunisal] vs. no previous tetramer stabilizer use
- Karnofsky Performance Status (KPS) [60; 70-80; 90-100]
- Cardiac Subpopulation (defined below)
- New York Heart Association (NYHA) Classification [I; II; III; IV]

The cardiac subpopulation will be comprised of patients with pre-existing cardiac amyloid involvement, defined as patients with baseline left ventricular (LV) wall thickness ≥ 1.3 cm and no aortic valve disease or hypertension in medical history.

Time in years since diagnosis with hATTR will be summarized using descriptive statistics. For those who previously used tetramer stabilizers, the time from discontinuation of tetramer stabilizer to the start of study drug will be summarized using descriptive statistics. The number and percent of patients with each genotype will be summarized by country and treatment group.

Continuous efficacy parameters will be summarized using descriptive summary statistics. The number and percent of patients in each category for PND score (I, II, IIIA, IIIB, IV) and FAP stage (I, II, III) will also be summarized.

Medical history will be summarized by system organ class (SOC), high level term (HLT), and preferred term. A patient contributes only once to the count for a given condition (overall, by SOC, by HLT, by preferred term).

All demographic and baseline data for each patient will be provided in data listings. Medical history data including prior neurological test scores, prior surgeries, and pregnancy test results will be presented in a data listing. Screening test results will also be presented in data listings.

4.3. Efficacy Evaluation

The primary efficacy analyses will be conducted using the mITT population. The primary endpoint mNIS+7 and the first secondary endpoint Norfolk QOL will also be evaluated for the PP population.

4.3.1. Primary Efficacy Evaluations

The primary efficacy endpoint is to compare change in mNIS+7 from baseline to Month 18 between treatment arms for the mITT population.

4.3.1.1. Primary Analysis using MMRM Method for the mITT Population

The primary analysis will be performed using a restricted maximum likelihood (REML) based MMRM approach. The outcome variable is change from baseline in mNIS+7. The model includes baseline mNIS+7 score as a continuous covariate and fixed effect terms including treatment arm, visit (Month 9 or Month 18), treatment-by-visit interaction, genotype (V30M vs. non-V30M), age at hATTR Symptom onset (< 50 ; ≥ 50), region (North America, Western Europe, and Rest of World), and previous tetramer stabilizer use (yes vs. no). An unstructured covariance structure will be used to model the within-patient errors. The Satterthwaite approximation will be used to estimate the degrees of freedom. The primary comparison is the contrast (difference in least squares means [LS means]) between the patisiran and placebo groups at 18 months. Analysis will be implemented with SAS PROC MIXED.

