9 STATISTICAL METHODS

9.1 Sample Size

Approximately 200 patients will be enrolled in this study. Of those 200 patients, no more than 40 patients will have a NIS range of 101 to 130. An mNIS+7 progression rate (primary endpoint) in the placebo group of 24 ± 16 points in 18 months was estimated using natural history data from FAP patients. A sample of 154 patients provides 90% power for a 2-sided test with an 8.95 point (37.5%) mean difference between treatment groups in the primary endpoint at 2-sided alpha = 0.05. Assuming a 25% random premature discontinuation rate (due to liver transplantation or other factors), the sample size for this study is approximately 200. Additional patients may be enrolled based on a recommendation to increase the sample size in the interim analysis.

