1.2.2. Randomization Methodology

Patients will be randomly assigned in a 2:1 ratio to receive either 0.3 mg/kg patisiran or placebo (normal saline 0.9%).

Patients will be randomized via an interactive response system (IRS). Either designated site personnel or the pharmacist may request randomization for the patient, but only the pharmacist or pre-identified unblinded personnel will be allowed to receive the randomized treatment code. The treatment code will be delivered to the unblinded personnel or the pharmacist to prepare the necessary number of vials for that patient based on their weight.

As described above in Section 1.2.1, the stratification factors for randomization include NIS (< 50 vs. ≥ 50), early onset V30M (< 50 years of age at onset) vs. all other mutations (including late onset V30M), and previous tetramer stabilizer use (tafamidis or diflunisal) vs. no previous tetramer stabilizer use.

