3. GENERAL STATISTICAL METHODS

3.1. Sample Size Justification

For the estimation of sample size, a mean (\pm SD) mNIS+7 progression rate (primary endpoint) in the placebo group of 24 ± 16 points over 18 months was estimated using natural history data [1] from FAP patients. A sample of 154 patients provides 90% power for a 2-sided t-test with an 8.95-point (37.5%) mean difference between treatment arms in the primary endpoint at 2-sided $\alpha = 0.05$. Assuming a 25% random premature discontinuation rate (due to liver transplantation or other factors), the required sample size for this study is approximately 200.

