3.8.3. Handling of Missing Data

For the primary and secondary efficacy endpoints, the primary analysis will be based on the mixed-effects model repeated measures (MMRM) method, which makes use of fully and partially observed data sequences from individual patients by estimating the covariance between data from different time points. The MMRM will be implemented using an unstructured approach to modeling both the treatment-by-time means and the (co)variances, leading to what is essentially a multivariate normal model wherein treatment arm means at the primary time point are adjusted to reflect both the actually observed data and the projected outcomes from the patients with missing data [11]. In this primary analysis, missing data will not be imputed and are assumed to be missing-at-random (MAR).

For the primary endpoint mNIS+7 and the first secondary endpoint Norfolk QOL, sensitivity analyses will be conducted to assess the impact of missing data as discussed in Section 4.3.

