4.3.2. Secondary Efficacy Evaluations

Secondary efficacy endpoints include Norfolk QOL-DN total score, NIS-W, R-ODS, 10-meter walk test speed, mBMI, and COMPASS-31. To control overall type I error, these endpoints will be tested in a hierarchical order as described in Section 3.6.

All the secondary endpoints are assessed at baseline, Month 9, and Month 18 with the exception of mBMI. mBMI is assessed at baseline, Day 84, Day 189, Day 357, Day 462 and Day 546. Day 546 will be used as Month 18 assessment.

For 10-meter walk test, the walk speed for patients unable to perform the walk will be imputed as 0. The change from baseline will then be calculated as 0 – baseline walk speed.

Change from baseline at Month 18 in the secondary efficacy endpoints will be analyzed for the mITT population, using an MMRM model similar to the model described for the primary analysis of mNIS+7 while adjusting for baseline value of the endpoint being modeled. For these secondary endpoints (except NIS-W), MMRM model will also include baseline NIS (< 50 vs. ≥ 50) as a factor. The MMRM model for NIS-W will not include baseline NIS since baseline NIS-W will be included as a covariate in the model.

For the first secondary endpoint Norfolk QOL-DN Total Score, the MMRM method will also be conducted for the PP population. In addition, sensitivity analyses will be conducted using ANCOVA/MI and including data post alternative treatment for FAP similar as described for mNIS+7 (see Section 4.3.1.3).

Month 18 change from baseline in mBMI will be estimated from the MMRM model using assessment results from all time points.

The planned analyses of the secondary endpoints are summarized in [Table 2](#).

Table 2 Analysis of Secondary Endpoints

Endpoint	Statistical Method	Analysis Population	Special Notes
Norfolk QOL-DN total score	Primary analysis: MMRM	mITT	
	Sensitivity analysis: 
 • MI/ANCOVA • MMRM - including Data Post Alternative Treatment for FAP 	mITT	
	Other analysis: MMRM	PP	
NIS-W	MMRM	mITT	Excludes data post alternative treatment for FAP
R-ODS	MMRM	mITT	
10-meter walk test speed	MMRM	mITT	For patients unable to perform the walk, walk speed imputed as 0
mBMI	MMRM	mITT	Measured at baseline, Day 84, Day 189, Day 357, Day 462 and Day 546
COMPASS-31	MMRM	mITT	

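### The primary MMRM uses one baseline mNIS+7 slope for Months 9 and 18; if the true slope differs by visit, the Month 18 contrast loses a little precision that a baseline-by-visit term would recover

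*SAP*

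**What the plan says.** SAP 4.3.1.1 defines the primary analysis as a REML-based MMRM of change from baseline in mNIS+7, with an unstructured within-patient covariance: "The model includes baseline mNIS+7 score as a continuous covariate and fixed effect terms including treatment arm, visit (Month 9 or Month 18"). It then lists treatment-by-visit, genotype, age at onset, region and previous stabilizer use. Baseline enters as a main effect, and no other section adds a baseline-by-visit term. The primary comparison is the difference in LS means at 18 months.

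SAP 3.8.3 says that the MMRM is "implemented using an unstructured approach to modeling both the treatment-by-time means and the (co)variances". SAP 4.3.2 analyses the secondary endpoints "using an MMRM model similar to the model described for the primary analysis" of mNIS+7, each with its own baseline value.

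The MI/ANCOVA and pattern-mixture sensitivity analyses in SAP 4.3.1.3 fit an ANCOVA to completed Month 18 data, so their baseline slope is specific to Month 18.

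**The concern.** With a single baseline coefficient, the model assumes that a one-point difference in baseline mNIS+7 shifts expected change by the same amount at both visits. If baseline severity is related to the rate of worsening, the shift at 18 months would be about twice that at 9 months. Protocol 1.4 makes some relation plausible: it chose the baseline NIS range so that the lower end would show progression and the upper end would avoid a ceiling effect.

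Under an unstructured covariance the common slope is determined almost wholly by the less variable Month 9 data. Any misfit then falls on Month 18, the visit of the primary contrast. What is at stake is precision. A second, smaller issue is that the primary and sensitivity analyses would differ in baseline adjustment as well as in missing-data handling, which blurs any comparison between them.

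**Working it through.** **The plan's own figure.** SAP 3.1 states: "A sample of 154 patients provides 90% power for a 2-sided t-test with an 8.95-point (37.5%) mean difference between treatment arms", with placebo progression "in the placebo group of 24 ± 16 points over 18 months". Protocol 9.1 gives the same difference "in the primary endpoint at 2-sided alpha = 0.05". Allocation is 2:1 (SAP 1.2.2).

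- Placebo n = (1.960 + 1.282)² × 16² × (1 + 1/2) / 8.95² = 50.4, rounded up to 51. With 102 on patisiran the total is 153.
- Noncentral-t power is 0.8999 at 153 and 0.901 at 154 (51:103), so 154 reproduces.
- With 25% discontinuation, 154 / 0.75 = 205.3, so 206, against approximately 200 planned.
- The calculation uses an unadjusted t-test with SD 16 and takes no credit for baseline adjustment.

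**Assumptions not in the documents.** Baseline mNIS+7 SD 40 (range 30–50). Month 18 slope b18 from 0 to 0.20 points per baseline point. Month 9 slope b9 equal to b18 or half of it. Month 9 SD 9. Residual correlation 0.5–0.7. The Month 18 SD of 16 is taken from the SAP.

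**Large-sample formula.** Let V9 and V18 be the residual variances after removing baseline, and C their covariance.

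- Weight of Month 9 in the common slope: w9 = (V18 − C) / (V9 + V18 − 2C); w18 = 1 − w9.
- Common slope: b = w9·b9 + w18·b18.
- SE ratio (common slope / by-visit slope): √[1 + (b18 − b)² × Var(baseline) / V18].

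*Slopes 0.05 and 0.10, correlation 0.7:* V9 = 81 − (0.05 × 40)² = 77. V18 = 256 − (0.10 × 40)² = 240. C = 0.7 × √(77 × 240) = 95.2. w9 = 144.8 / 126.7 = 1.14 and w18 = −0.14. b = 0.043. The misfit variance is (0.057 × 40)² = 5.2. Ratio = √(1 + 5.2/240) = 1.011.

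*Slopes 0.025 and 0.05, correlation 0.5:* V9 = 80, V18 = 252, C = 71.0. w9 = 181.0 / 190.0 = 0.95. b = 0.026. The misfit variance is (0.024 × 40)² = 0.9. Ratio = √(1 + 0.9/252) = 1.002.

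**Simulation.** Two-visit REML MMRM, N = 200 (133:67), 25% random missingness at Month 18 ("Assuming a 25% random premature discontinuation rate (due to liver transplantation or other factors"), true difference 8.95, baseline SD 40, 500 runs per scenario. The other covariates were left out. Ratios come from unrounded standard errors.

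| Slopes M9 / M18 | Corr. | Large-sample ratio | SE common / by-visit | Simulated ratio | Power common / by-visit |
|---|---|---|---|---|---|
| 0 / 0 | 0.7 | 1.000 | 2.578 / 2.583 | 0.998 | 0.958 / 0.950 |
| 0.05 / 0.05 | 0.7 | 1.000 | 2.565 / 2.571 | 0.998 | 0.940 / 0.940 |
| 0.025 / 0.05 | 0.7 | 1.003 | 2.562 / 2.560 | 1.001 | 0.930 / 0.930 |
| 0.05 / 0.10 | 0.5 | 1.008 | 2.619 / 2.603 | 1.006 | 0.908 / 0.916 |
| 0.05 / 0.10 | 0.7 | 1.011 | 2.534 / 2.513 | 1.009 | 0.934 / 0.944 |
| 0.10 / 0.20 | 0.5 | 1.036 | 2.408 / 2.320 | 1.038 | 0.966 / 0.980 |
| 0.10 / 0.20 | 0.7 | 1.052 | 2.361 / 2.248 | 1.050 | 0.968 / 0.978 |

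Mean estimates under the common slope ran from −8.79 to −9.10 against a true −8.95. The simulation error of each mean is about 2.6/√500 = 0.12. The two models differed by at most 0.07 within a scenario.

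**More extreme cases.** Baseline SD 50 with slopes 0.10/0.20 gives large-sample ratios of 1.066 (correlation 0.5) and 1.095 (0.7). A separate simulation used baseline SD about 38, residual SDs 10 and 15, and dropout depending on Month 9. With the slope tripling (0.05/0.15), the standard error was 2.429 against 2.365, a ratio of 1.027. With a fivefold slope (0.05/0.25) it was 2.614 against 2.367, a ratio of 1.104. The fivefold case implies a Month 18 SD of √(15² + (0.25 × 38)²) = 17.8, above the planned 16. The change in bias was below 0.1 point.

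**The case against.** A reader might infer that, because mNIS+7 change accumulates over 18 months, the written model necessarily has an inflated Month 18 standard error. The documents do not support that. Accumulating mean change is already free through visit and treatment-by-visit. A loss requires a non-zero baseline slope that changes between visits, and neither document reports one.

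A reader might also see SAP 3.8.3 as contradicting SAP 4.3.1.1. It does not: the unstructured approach there covers treatment-by-time means and covariances, not the baseline slope. A main-effect baseline is a valid specification.

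Extending the loss to every secondary endpoint is also unsupported. None was simulated, each uses its own baseline, and most add a baseline NIS category.

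These points stand, and they limit the concern to a conditional one. Two others carry less weight. The Month 18 ANCOVA sensitivity analyses do free the slope, but they are not the primary test. Another model change after SAP V2.0 went to the Agency has some procedural cost, but V2.1 made a further analysis change (censoring for NIS-W), so small edits were still being accepted.

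**Conclusion.** The concern holds as a modest, conditional efficiency point. The model as written has one baseline slope for both visits. If the true slopes differ, the Month 18 standard error is larger than it needs to be; if they are equal, nothing is lost. Under the assumed doubling with baseline SD 40 and correlation 0.5–0.7, the excess is about 0.2% to 5%, and about 1% at a Month 18 slope of 0.10. Only wider baseline spread or steeper slope growth takes it to roughly 7–10%.

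The validity of the primary test is not threatened. The estimates show no bias beyond simulation error, and simulated power exceeds 90% in every scenario tabulated. The lowest value is 0.908, with a simulation error of about √(0.908 × 0.092/500) = 0.013. Where the slope doubles, power changes by 0 to 1.4 percentage points. All magnitudes rest on the assumed baseline SD, slopes, Month 9 SD and correlation.

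**What to change.** Before unblinding, add a baseline mNIS+7-by-visit interaction to the primary MMRM in SAP 4.3.1.1 and record it in SAP Section 5. The baseline slope at Month 18 is then visit-specific, as in the MI/ANCOVA and pattern-mixture analyses, so differences between primary and sensitivity results reflect missing-data handling more cleanly.

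The same term can be added to the secondary MMRMs for consistency, without claiming a gain that has not been quantified.

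The cost is one degree of freedom for two visits and four for mBMI (five post-baseline visits, 5 − 1 = 4). If the slopes are in fact equal, the primary standard error rises by about 0.2% (2.578 to 2.583). No new data are needed. This is a near-free improvement, not a correction of an error.

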
Other Assessments
	
Disease burden and healthcare utilization will be assessed using a patient-reported pharmacoeconomics questionnaire. The investigator will periodically assess mental status as it relates to suicidal ideation and behavior by using the Columbia–Suicide Severity Rating Scale (C-SSRS) questionnaire.

Follow-Up
	
Patients who complete the 18-month efficacy assessments can elect to participate in an extension study in which patients would receive open-label administration of 0.3 mg/kg patisiran once every 21 days. Eligible patients who elect to participate will return for a follow-up visit 21 days after last dose of study drug.
 
If the patient decides not to participate in the extension study, the patient will complete 2 follow-up visits at 21 and 56 days after the last dose of study drug. Each follow-up visit includes safety assessments and the 21-day follow-up also includes PD measurements.

Statistical Methods
	
A full statistical analysis plan (SAP) will be finalized prior to database lock.
 
The primary analysis will compare patients administered patisiran versus those administered placebo in the modified intent-to-treat (mITT) population. Specifically, patients who are randomized and receive at least 1 dose of study drug will be included in this analysis. The primary analysis will compare change in mNIS+7 from baseline at 18 months between patisiran and placebo groups, adjusted for the stratification factors. Analysis of covariance (ANCOVA) will be used to analyze the primary endpoint. Primary endpoint data that are missing will be inferred using multiple imputations. Sensitivity analyses, including mixed model repeated measures (MMRM) analyses, will assess the robustness of the primary analysis for the mITT and per protocol (PP) populations.
 
Type I error control for secondary endpoints will be achieved by a hierarchical ordering procedure. Briefly, endpoints will be evaluated in order to control for multiplicity.
 
An independent interim analysis committee (IAC) will conduct a blinded interim analysis when approximately 50% of patients have completed their 9-month mNIS+7 assessments. This

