3.5. Randomization Stratification Factors

Stratification factors for randomization include Neuropathy Impairment Score (NIS; < 50 vs. ≥ 50), early onset V30M (< 50 years of age at onset) vs. all other mutations (including late onset V30M), and previous tetramer stabilizer use (tafamidis or diflunisal) vs. no previous tetramer stabilizer use.

Stratification factors are recorded in both the IVR and the clinical database. In statistical analyses that use randomization stratification factors as covariates, the stratum assignment will reflect the values as recorded in the clinical database. In the presence of stratification errors, the stratification used in analysis may not match that in the IVR.

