5.4. Adjustment for Covariates in Statistical Models

The table below summarizes the history of changes in baseline covariates used in the statistical models.

Baseline Covariates	Protocol	SAP V1.0	SAP V2.0
	ANCOVA	ANCOVA	MMRM/ANCOVA
Baseline mNIS+7	X	X	X
Genotype (V30M vs. Non-V30M)	X		X
Genotype class (early onset V30M vs. Other)		X	
Age at hATTR symptom onset (< 50 vs. ≥ 50)			X
Previous tetramer stabilizer use (Yes vs. No)	X	X	X
Region (Western EU, North America, Rest of World)			X
Age at study entry as continuous variable	X		

Genotype class (early onset V30M vs. other) is one of the stratification factors at randomization. The early onset V30M subgroup includes patients who have the V30M genotype and were younger than 50 years old at hATTR amyloidosis symptom onset. At the time of this SAP amendment, the enrollment was complete and there were only 23 early onset V30M patients. Given the small sample size, the composite covariate “genotype class” is decomposed into 2 separate covariates “genotype” and “age at hATTR amyloidosis symptom onset.”

Region is added as a covariate because different rates of attrition and disease worsening were observed for different regions during blinded data monitoring. In addition, adding region may potentially address the influence of different non-V30M types observed across regions.

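### The primary mNIS+7 model does not adjust for two of the three randomisation factors in the form used to randomise, and this does not match the protocol synopsis

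*SAP*

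**What the plan says.** SAP 3.5 opens "Stratification factors for randomization include Neuropathy Impairment Score" and goes on to early-onset V30M vs all other mutations and previous tetramer stabilizer use. It adds that, where these factors serve as covariates, the clinical-database values are used.

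The Statistical Methods part of the protocol synopsis describes the primary comparison as "adjusted for the stratification factors". Protocol 9.2.3.1, the detailed specification, lists baseline mNIS+7, age, genotype, prior stabilizer use and treatment.

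SAP 4.3.1.1 replaces that ANCOVA by an MMRM with baseline mNIS+7 (continuous), treatment, visit, "treatment-by-visit interaction, genotype (V30M vs. non-V30M), age at hATTR Symptom onset" (cut at 50), region and previous stabilizer use. The ANCOVAs for the MI and PMM analyses (SAP 4.3.1.3) use the same baseline terms.

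SAP 5.4 explains that, with only 23 early-onset V30M patients enrolled, the composite genotype class "is decomposed into 2 separate covariates". It does not mention NIS category. For the secondary endpoints other than NIS-W, SAP 4.3.2 states that the "MMRM model will also include baseline NIS" at the same cut of 50.

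**The concern.** When randomisation is balanced on a factor that predicts outcome, a model without that factor leaves its variance in the residual. The estimated treatment effect is then less variable than the model standard error implies, and the test tends to be conservative. Adjusting for the factors used to randomise removes this at little cost.

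Here only previous stabilizer use enters the primary model in its randomised form. A reader of the synopsis would expect all three. No listed mNIS+7 analysis shows whether the result survives adjustment for the full design. At stake are a little precision and consistency between the protocol's two statements and the SAP.

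**Working it through.** **1. The plan's own sample size.** SAP 3.1 states "A sample of 154 patients provides 90% power for a 2-sided t-test" and takes the placebo progression as "24 ± 16 points over 18 months was estimated using natural history data". Inputs: difference 8.95, SD 16, two-sided alpha 0.05, power 90%, allocation 2:1.

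- Placebo n = (1 + 1/2) × 16² × (1.960 + 1.282)² / 8.95² = 50.4, rounded up to 51, so 153 in total.
- A noncentral t calculation with 103 and 51 patients gives 90.1% power; the normal approximation at 154 gives 90.5%.
- 154 / 0.75 = 205.3, rounded up to 206, consistent with approximately 200.

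The figure reproduces, so SD 16 and N = 154 are a fair base for sizing this point.

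**2. The covariate sets side by side.**

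| Randomisation factor | Protocol 9.2.3.1 | SAP V1.0 (per SAP 5.4) | Primary MMRM and matching ANCOVAs | Secondary MMRMs |
|---|---|---|---|---|
| NIS <50 / ≥50 | no | no | no | yes, except NIS-W |
| Early-onset V30M vs other | genotype only | yes | genotype and onset age, additive | as primary |
| Previous stabilizer use | yes | yes | yes | yes |

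The remaining mNIS+7 sensitivity analyses and the PP analysis (SAP Table 1) reuse the MMRM. The binary analyses are stratified by genotype alone.

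**3. Why two additive terms are not the stratum.** Let G = 1 for V30M and A = 1 for onset before 50. The stratum is E = G × A. If E shifts the outcome by γ, then μ11 − μ10 − μ01 + μ00 = γ, whereas the additive model forces this contrast to 0. The main effects absorb part of γ; the rest stays in the residual.

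**4. How much variance could be at issue.** The documents give no stratum effects, so a range is shown.

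- Early-onset V30M: the share of variance is at most γ²p(1 − p)/16², with p = 23/200 = 0.115 (200 enrolled is assumed). This is 1.0% at 5 points and 4.0% at 10, before crediting the two main effects already fitted.
- NIS category: b² × 0.25 × (1 − ρ²)/16², with half the patients on each side of 50 and ρ the assumed correlation of category with baseline mNIS+7. For ρ = 0.85 and 0.7 this is 0.7% and 1.2% at 5 points, and 2.7% and 5.0% at 10.
- With SD = 16√(1 − R²), extra R² of 0, 1, 2, 4 and 10% gives power of 90.5, 90.8, 91.1, 91.6 and 93.2% at N = 154.

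**5. Simulation, single-visit ANCOVA.** 4,000 trials per cell, N = 154, stratified 2:1 blocks. The two residual effects have equal size and opposite sign. The standard errors and type I error come from the runs with no treatment effect, and power from the runs with a difference of 8.95.

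| Points per omitted term | SE, SAP terms | SE, both added | Change | Power, SAP terms | Power, both added | Type I error, SAP terms |
|---|---|---|---|---|---|---|
| 0 | 2.773 | 2.784 | +0.4% | 89.0% | 88.6% | 4.8% |
| 5 | 2.794 | 2.783 | −0.4% | 89.4% | 89.2% | 4.7% |
| 10 | 2.864 | 2.784 | −2.8% | 88.0% | 89.1% | 5.1% |
| 15 | 2.972 | 2.785 | −6.3% | 86.5% | 89.6% | 4.2% |

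The Monte Carlo error of one power figure is √(0.89 × 0.11 / 4000) = 0.5 points, so the power differences in the first two rows should not be interpreted. Assumptions: mean NIS 60 (SAP 5.5 gives approximately that), NIS SD 35, NIS–mNIS+7 correlation 0.9, V30M 43%, stabilizer use 50%, equal regions, block size 6, residual SD 16, no missing data.

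**6. Simulation, two-visit MMRM.** N = 200, Month 18 residual SD 15, dropout depending on Month 9, 700 runs per scenario.

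- 6 points (NIS) and 8 points (early-onset V30M): SE 2.451 to 2.429, −0.9%.
- 10 points for early-onset V30M only: 2.400 to 2.384, −0.7%.
- No effect: 2.429 to 2.433, +0.2%.

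The adjusted standard errors differ between scenarios (2.384 to 2.433) by more than any of these gains, so only the within-scenario changes should be read.

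**The case against.** Most of the prognostic information is already in the model. Baseline mNIS+7 is continuous and contains NIS-W (192) and NIS-R (20), which is 212 of the 244 NIS points (192 + 20 + 32); a continuous score normally carries more than a cut at 50. The SAP leaves NIS category out of the NIS-W model because baseline NIS-W is already a covariate, and the same logic would fit mNIS+7. The other secondary endpoints have no neuropathy score as their baseline covariate, so adding NIS there is coherent. Both parts of early-onset V30M are in the model, and the split is declared with a reason. Protocol 9.2.3.1 has neither NIS category nor the early-onset class, and the SAP 5.4 history has no NIS row, so no NIS term was removed. Both factors are also prespecified mNIS+7 subgroups (SAP 4.3.4).

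Much of this stands. It keeps the likely gain small and shows that the conflict lies first inside the protocol, between synopsis and section 9.2.3.1. Two parts do not settle the matter. The SAP never applies the NIS-W reasoning to mNIS+7. And 23 patients is a weak reason against one fixed effect estimated from the whole trial when SAP 4.3.4 plans a model within that same stratum.

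A reader might also infer that patients are not analysed as randomised. The documents do not support that: SAP 2.1 analyses the mITT population by randomised arm. The point concerns covariates only.

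**Conclusion.** The mismatch is clear from the text: the primary MMRM and the matching ANCOVAs omit NIS category without a reason, represent early-onset V30M only additively, and do not do what the synopsis says.

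The statistical consequence is small. The standard error is likely under 1% too large for modest residual stratum effects and about 3% (about one power point) if each omitted term carried 10 points beyond the included covariates. If they carry nothing, adding them costs 0.2–0.4%. These sizes rest on assumed effects and on the simulation settings listed above.

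Two stronger readings are tempting. One is that the primary test is invalid: simulated type I error under the SAP terms was 4.2–5.1%, with no sign of inflation. The other is that precision is certainly being lost: the documents give no stratum effects, so a material loss is possible but not shown. Nor is it accurate to say that both factors are simply left out, since genotype, onset age and a closely related severity score are all fitted.

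**What to change.** Before unblinding, add baseline NIS (<50 vs ≥50) and the genotype-by-onset-age interaction (equivalently, with both main effects kept, an early-onset V30M indicator) as fixed effects to the primary MMRM and to the ANCOVAs in the MI and PMM analyses. Keep the existing terms, and take stratum values from the clinical database as SAP 3.5 already directs.

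At minimum, prespecify one sensitivity MMRM for mNIS+7 with all three randomisation factors and state why NIS category is not in the primary model.

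In either case, reconcile the synopsis wording with protocol 9.2.3.1 and SAP 4.3.1.1, and record the decision in SAP 5.4.

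The cost is SAP wording and two degrees of freedom, with no new data. The downside is the 0.2–0.4% increase in standard error if the two terms turn out not to be prognostic.
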